Long-term storage of specimens will be at -80° C. The samples will be stored in a designated freezer housed at Pennington Biomedical Research Center. The Principal Investigator, unless otherwise noted, will be the person who has access to the samples. Each sample will be labeled with the subject's ID and date.

Power analysis

After completion of baseline measurements, participants will be stratified by sex (male vs female) and then randomized in a 1:1 ratio to either the exercise or control group using a computer-generated algorithm. The co-primary outcomes for this study are hs-CRP and IL-6. For the CRP outcome, assuming a baseline concentration of 1.87 mg/L with a standard deviation of 1.32 mg/L, correlation of 0.8 between time points, a reduction of -0.71 mg/L in the exercise group over 12 weeks, and a type-I error rate of 5%, 46 participants total will provide 80% statistical power to detect between-group differences. For the IL-6 outcome, assuming a baseline concentration of 1.7 pg/mL with a standard deviation of 0.7 pg/mL, a correlation of 0.58 between time points, a reduction of -0.57 pg/mL in the exercise group over 12 weeks, and a type-I error rate of 5%, 48 participants will provide 80% statistical power to detect between-group differences. sTNF- α R2 is a secondary inflammatory measure. In the pilot study, we observed a 3% dropout rate (defined as participants not providing endpoint data), an 8% crossover rate (defined as control group participants who disclose initiating a structured, progressive exercise program during the trial), and 8% recurrence rate (defined as the clinical discovery of locoregional or distant metastatic disease).⁷⁰ We will inflate these estimates to accommodate a higher-than-anticipated dropout, experience a recurrence, and/or crossover. Enrolling 60 study participants provides a robust estimate of the largest necessary sample size needed for this trial. This sample size provides adequate statistical power to detect moderate between-group effect size differences (e.g., Cohen's d of ≥ 0.3) for measures of insulin resistance (Aim 2) and CTCs (Aim 3).

Statistical Analysis

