The primary hypothesis in this trial is that exercise will significantly lower plasma inflammation concentrations over 12 weeks compared to control. All inferential analyses will be conducted on an intention-to-treat basis. Plasma inflammatory concentrations will be log-transformed in the inferential analysis to improve normality. Changes in outcomes will be evaluated from baseline to follow-up in the two groups using a repeated-measures mixed-effects regression model that accounts for the correlation between repeated measures and is robust to missing data. The baseline value of the dependent variable and sex (randomization stratification factor) will be included as a covariate in the regression models.⁵⁵ Group-by-time interaction terms will be included as fixed effects in the regression model. Model fit will be assessed using standard methods. A closed testing procedure for the two study outcomes (hs-CRP and IL-6) will be used, which is hierarchically ordered to test CRP and then IL-6 to maintain the overall experiment-wise error rate at 5%.⁵⁶ Other inflammatory outcomes and measures of insulin resistance (Aim 2) and CTCs (Aim 3) will be analyzed using the same statistical techniques and reported at the nominal type I error rate of 5%.

Data and Specimen Management

Study participants will be assigned unique subject identification (ID) numbers. Study subject ID numbers will be used on all data collection instruments, including questionnaires, data collection forms, biological specimen tubes, and computer records. A master list linking the participants' names and ID numbers will be kept in a password-protected computer file with access restricted to the PI and co-PIs. Biological samples that are moved off-site for analysis will not contain any personally identifiable information and will be labeled with only the unique subject ID numbers. Staff at these sites will not have access to the master list at any time.

Data collection forms will be kept under lock and key or password-protected if computerized and under the control of the PI, co-PIs, and medical investigator. Only personnel assigned to the research study by the PI will have access to the data. Hard-copy data records will be stored for a minimum of three years after study completion.

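### The 80% power stated for IL-6 at 48 participants is that of the IL-6 test alone; under the planned hs-CRP-then-IL-6 order, the power to claim IL-6 is lower (about 70–78% at 48 on the printed inputs, assuming test statistics correlated 0 to 0.8)

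*Combined protocol and SAP*

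**What the plan says.** The Power analysis section states that "The co-primary outcomes for this study are hs-CRP and IL-6" and then sizes each outcome separately at a 5% type I error.

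- For hs-CRP the inputs are "assuming a baseline concentration of 1.87 mg/L with a standard deviation of 1.32 mg/L, correlation of 0.8 between time points" and a fall of 0.71 mg/L with exercise. The result is 46 participants for 80% power.
- For IL-6 the inputs are "assuming a baseline concentration of 1.7 pg/mL with a standard deviation of 0.7 pg/mL, a correlation of 0.58 between time points" and "a reduction of -0.57 pg/mL in the exercise group over 12 weeks". The conclusion is that "48 participants will provide 80% statistical power to detect between-group differences".

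Enrolment is then set at 60. The reasons given are dropout, crossover and recurrence, for which the pilot rates were 3%, 8% and 8%.

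The Statistical Analysis section describes a closed testing procedure that is "hierarchically ordered to test CRP and then IL-6 to maintain the overall experiment-wise error rate at 5" per cent. It also puts the baseline value of the outcome into the model as a covariate. The power section does not mention the test order, the joint power, or a figure for the correlation between the two outcomes.

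**The concern.** Under a fixed order, a significant IL-6 result counts only if hs-CRP was significant first. The power to claim IL-6 is then the probability that both tests succeed. It cannot exceed the smaller of the two separate powers, and with two tests near 80% it falls below 80% unless they succeed and fail almost together.

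IL-6 is a named co-primary outcome. A reader of the power section would take 48 completers as enough for an 80% chance of claiming it, and would see 60 − 48 = 12 participants in reserve. The ordered procedure uses part of that reserve, although the section assigns all of it to dropout, crossover and recurrence.

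**Working it through.** **Assumptions.** The test is two-sided at 5% (the plan does not give sidedness), allocation is 1:1, the control group does not change, and the scale is raw as in the power section. Power for each test alone comes from the noncentral t distribution. The correlation ρ between the two test statistics is not in the documents; the range used is 0 to 0.8.

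**Step 1: hs-CRP, plan's figure.** SD of change = 1.32 × √(2 × (1 − 0.8)) = 0.835, so d = 0.71 / 0.835 = 0.850. Power is 80.5% at 46, which reproduces the plan. It is 82.2% at 48 and 88.9% at 58.

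**Step 2: IL-6, plan's figure.** SD of change = 0.7 × √(2 × (1 − 0.58)) = 0.642, so d = 0.57 / 0.642 = 0.888. Power is 85.4% at 48 and 91.4% at 58, and 42 participants would give 80%. The plan's 48 and 80% do not reproduce from these inputs. They come out only if the correlation is left out: with SD 0.7, the normal approximation gives N = 48 and 80.5%, and the t calculation gives N = 50. Both versions are therefore carried forward: the printed inputs (d = 0.888), and the stated 80% at 48 taken at face value (d = 0.826, which gives 87.1% at 58).

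**Step 3: power under the ordered procedure.** P(both significant) = Φ₂(Φ⁻¹(p₁), Φ⁻¹(p₂); ρ), where p₁ and p₂ are the separate powers. At ρ = 0 this is the product: 0.822 × 0.854 = 0.702 on the printed inputs, and 0.822 × 0.800 = 0.658 on the stated power.

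| Evaluable N and basis | IL-6 alone | ρ = 0 | ρ = 0.5 | ρ = 0.8 |
|---|---|---|---|---|
| 48, printed inputs | 85.4% | 70.2% | 74.0% | 77.5% |
| 48, stated 80% | 80.0% | 65.8% | 70.2% | 74.2% |
| 58, printed inputs | 91.4% | 81.3% | 83.4% | 85.7% |
| 58, stated 80% | 87.1% | 77.4% | 80.2% | 83.0% |
| N for 80%, printed inputs | – | 58 | 54 | 52 |
| N for 80%, stated 80% | – | 62 | 58 | 56 |

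The 58 is 60 less the pilot's 3% dropout (60 × 0.97 = 58.2).

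**Step 4: baseline adjustment.** With full credit for the planned covariate, the residual SDs are 1.32 × √(1 − 0.8²) = 0.792 and 0.7 × √(1 − 0.58²) = 0.570. Separate powers at 48 become 86.0% and 92.4%, and power under the ordered procedure is 79.4%, 81.7% and 83.9% at ρ = 0, 0.5 and 0.8.

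**Step 5: reserve within 60.** On the printed inputs it is 60 − 58 = 2 to 60 − 52 = 8. On the stated power it is 60 − 62 = −2 to 60 − 56 = 4. The power section implies 12.

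**The case against.** Four points on the other side have force.

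- **Separate power per endpoint is a common way to report.** Read literally, the sentence is about detecting a difference in IL-6, not about claiming it through the hierarchy. That is fair, and it is why the remedy is to label the figure and add to it. But the document sets a test order and names IL-6 co-primary, and it gives no other power for that outcome.
- **The planned model adjusts for baseline.** With full credit, power under the ordered procedure at 48 is about 79–84%, so the shortfall against 80% nearly disappears. This stands as a possible outcome. However, the 46 for hs-CRP matches an unadjusted change-score calculation, so the power section does not itself rely on that gain. Even then the ordered figure is well below the 92% for IL-6 alone.
- **The trial enrols 60, not 48.** On the printed inputs, power under the ordered procedure is 83–87% at 60. This stands too. But the extra participants were justified by dropout, crossover and recurrence, and under intention-to-treat the last two may dilute the effect.
- **The correlation is assumed.** The Background calls the correlation between CRP and IL-6 strong but gives no number, so ρ = 0 is the least supported end. Every change-score value at 48 is nevertheless below 80% across the range, including at 0.8.

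A reader might infer that the trial is underpowered for IL-6, or that its true power is 66–74%. The documents do not support either. The 66–74% range applies to 48 rather than the planned 60, and it depends on a stated 80% that the printed inputs do not reproduce. Nor is there a problem with type I error: the fixed order controls it.

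**Conclusion.** Wrong as written, and modest in size. The 80% at 48 is the power of the IL-6 test alone. On the change-score basis that reproduces the hs-CRP figure, the power to claim IL-6 at 48 is about 70–78% (printed inputs) or 66–74% (stated 80%). With full baseline adjustment it is about 79–84%. Reaching 80% on the change-score basis takes about 52–58 evaluable participants on the printed inputs, or 56–62 on the stated power, rather than 48.

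The planned 60 roughly retains 80%, with less reserve than the power section suggests. The figures rest on the assumed correlation of 0 to 0.8, a two-sided test, no change in controls and the raw scale, although the analysis is planned on the log scale. None of them allows for dilution from crossover or recurrence. The power statement for hs-CRP, which is tested first, is unaffected.

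**What to change.** Keep the sample size, the test order and the analysis. In the Power analysis section:

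1. Label the 80% at 48 as the power of the IL-6 test considered alone.
2. Add the power to claim IL-6 under the hs-CRP-then-IL-6 order, at 48 and at the planned size after dropout, with the assumed correlation of the test statistics stated. On the printed inputs that is about 70–78% at 48 and 81–86% at 58, for correlations of 0 to 0.8. Say whether the figures credit the baseline adjustment.
3. Reconcile the 48 and 80% with "a correlation of 0.58 between time points": either correct the inputs or restate the figure, since the printed inputs give about 85% at 48. If the stated 80% is what was intended, the ranges in item 2 become 66–74% and 77–83%.

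The cost is a few sentences and a less favourable stated figure for IL-6. No extra participants are needed.

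### Sixty participants do not give adequate power for a Cohen's d of 0.3 on insulin resistance and CTCs: two-sided power is 21% unadjusted, and 29% or 48% at correlations borrowed from IL-6 and hs-CRP

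*Combined protocol and SAP*

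**What the plan says.** The Power analysis section justifies the sample size on the two co-primary outcomes and then extends the justification to the secondary aims. After giving 46 participants for hs-CRP and 48 for IL-6, each at 80% power, it states: "Enrolling 60 study participants provides a robust estimate of the largest necessary sample size needed for this trial". The next sentence reads "This sample size provides adequate statistical power to detect moderate between-group effect size differences", with the size of effect given as "e.g., Cohen's d of ≥ 0.3) for measures of insulin resistance (Aim 2) and CTCs (Aim 3". No power percentage, standard deviation, correlation or sidedness is given for these two aims.

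Participants are "randomized in a 1:1 ratio to either the exercise or control group", so there are 30 per arm. The Statistical Analysis section includes the baseline value of the outcome and sex as covariates, and says that Aims 2 and 3 "will be analyzed using the same statistical techniques and reported at the nominal type I error rate of 5" percent.

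**The concern.** A two-arm comparison with 30 per group does not normally detect a difference of 0.3 SD with useful power. The same paragraph points the same way. The planned hs-CRP effect is 0.71/1.32 = 0.54 SD, and 46 participants are said to be needed for 80% power at a correlation of 0.8. Required N varies roughly with 1/d², so going from 0.54 to 0.3 at the same correlation multiplies it by about (0.54/0.3)² = 3.2. Sixty cannot then be enough.

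At stake is how the secondary results are read. Someone who relies on the sentence could take a non-significant result for insulin resistance or CTCs as evidence against an effect of 0.3 SD, which the trial cannot provide.

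**Working it through.** **Inputs.** From the Power analysis section: N = 60, 1:1 allocation, d = 0.3, 5% type I error, 80% as the power level used for the co-primaries, and 3% dropout in the pilot. The correlations are 0.8 for hs-CRP ("correlation of 0.8 between time points, a reduction of -0.71 mg/L in the exercise group over 12 weeks") and 0.58 for IL-6 ("a correlation of 0.58 between time points, a reduction of -0.57 pg/mL in the exercise group over 12 weeks"). From the Statistical Analysis section: a baseline-adjusted model.

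**The plan's own figures first.** The comparison is a two-sample t-test, with power from the noncentral t distribution.

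- hs-CRP: SD of change = 1.32 × √(2 × (1 − 0.8)) = 0.835, and standardised effect = 0.71/0.835 = 0.85. For 80% power the total N is 46 two-sided and 36 one-sided. The stated 46 is reproduced as a two-sided test on change scores.
- IL-6: SD of change = 0.7 × √(2 × (1 − 0.58)) = 0.642, and standardised effect = 0.57/0.642 = 0.89. Total N is 42, not 48. The stated 48 appears only if the correlation is ignored (0.57/0.7 = 0.81) and a normal approximation is used.

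Two-sided testing is therefore supported by the hs-CRP figure. It is an assumption for Aims 2 and 3, so one-sided results are shown as well.

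**Power at d = 0.3.** The standardised effect is d unadjusted and d/√(1 − r²) with baseline adjustment, with df = N − 2. The noncentrality is that effect × √(N/4). At N = 60:

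- unadjusted: effect 0.300, noncentrality 0.300 × 3.873 = 1.16
- r = 0.58: 0.3/0.8146 = 0.368, noncentrality 1.43
- r = 0.8: 0.3/0.6 = 0.500, noncentrality 1.94

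| Setting | Unadjusted | r = 0.58 | r = 0.8 |
|---|---|---|---|
| N = 60, two-sided 5% | 20.8% | 28.9% | 47.8% |
| N = 58 (pilot's 3% dropout) | 20.2% | 28.1% | 46.5% |
| N = 48 (assumed 20% loss) | 17.4% | 23.9% | 39.6% |
| N = 60, one-sided 5% | 31.0% | 40.7% | 60.6% |

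A change-score analysis, with effect d/√(2(1 − r)), gives 23.9% at r = 0.58 and 43.9% at r = 0.8 (N = 60, two-sided). Baseline adjustment, which is what the plan specifies, is the more favourable of the two.

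**What d = 0.3 would need.** At N = 60, two-sided, with baseline adjustment, 50% power requires r of about 0.81 and 80% power requires r of about 0.91. Holding r fixed, the total N for 80% power is 352 unadjusted, 234 at r = 0.58 and 128 at r = 0.8.

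**What the trial can detect at 80% power, two-sided.**

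| Evaluable N | Unadjusted | r = 0.58 | r = 0.8 |
|---|---|---|---|
| 60 | 0.74 | 0.60 | 0.44 |
| 58 | 0.75 | 0.61 | 0.45 |
| 48 | 0.83 | 0.67 | 0.50 |

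**Precision.** The half-width of the 95% confidence interval for the group difference, in SD units, is t(0.975, 58) × √(4/60) × √(1 − r²) = 2.002 × 0.2582 × √(1 − r²). This gives 0.517 unadjusted, 0.421 at r = 0.58 and 0.310 at r = 0.8.

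**The case against.** The plan says only that power is adequate and gives no percentage for Aims 2 and 3; 80% is carried over from the co-primaries. That is correct. But 80% is the only level the plan uses, it stands in the same paragraph, and at the plan's correlations two-sided power stays below 50%.

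The correlations of 0.58 and 0.8 belong to other outcomes, so 29% and 48% are illustrations. That also stands. A higher correlation for insulin resistance or CTCs would raise power, but about 0.91 would be needed and nothing in the documents suggests it.

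Other readings of the sentence do not rescue it. If d is standardised by the SD of change, the unadjusted 21% applies directly to a change-score comparison. If 0.3 was meant as Cohen's f (d = 0.6), unadjusted power is 63%, and the text says d. Larger effects fall within the stated range, but the claim begins at 0.3.

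Three limits should be kept in view:

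- The IL-6 total does not reproduce by the method that reproduces hs-CRP, so two-sidedness is inferred from one outcome of two. The conclusion holds either way.
- The interval around a zero estimate includes 0.3 only narrowly at r = 0.8 (0.310 against 0.300) and would exclude it from r just above 0.81.
- CTCs are cell counts, so a normal-theory d is only an approximate guide for Aim 3.

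Finally, the aims are secondary and do not set N. That limits the consequence but does not make the statement correct.

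**Conclusion.** The statement is wrong as written. At d = 0.3 with 60 participants, two-sided power is 21% unadjusted, 29% at r = 0.58 and 48% at r = 0.8. The most favourable variant at the plan's correlations (one-sided, r = 0.8, no dropout) reaches 61%. The result rests on 30 evaluable per arm, a normal-theory comparison of means, d standardised by the outcome SD, and correlations borrowed from IL-6 and hs-CRP.

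This does not show that the aims are underpowered for larger effects. If the ± values in the Preliminary Data section are standard errors with n = 12 to 14 (an assumption), the pilot's within-group change is 28.0/(8.4 × √n) = 0.89 to 0.96 SD of change for fasting insulin and 1.3/(0.3 × √n) = 1.16 to 1.25 for CTCs. Those are 24-week, within-group results, and fasting insulin is not the OGTT area under the curve, so they are context only. The error lies in the figure of 0.3. It should be corrected, but it affects neither the primary analysis nor the sample size.

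**What to change.** Replace the sentence in the Power analysis section with the effect detectable at 80% power, for example:

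> With 60 participants and a two-sided 5% test, the trial has 80% power for a between-group d of about 0.74 without baseline adjustment. If the baseline to month-3 correlation for insulin resistance and CTCs equals that assumed for IL-6 (0.58) or hs-CRP (0.8), the detectable d is about 0.60 or 0.44. If 48 participants (20% loss) are evaluable, these figures are 0.83, 0.67 and 0.50.

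Say that the correlations are borrowed assumptions and that the 20% loss is illustrative, and note that the figures are approximate for a count outcome such as CTCs. Add to the Statistical Analysis section that Aims 2 and 3 are reported with 95% confidence intervals and that a non-significant result is not read as ruling out d = 0.3.

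The aims, the planned 5% tests and enrolment do not change. The cost is one restated sentence, a line on reporting, and a less favourable stated detectable effect.

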- b. Usual Care Control Group. Participants randomized into the wait-list control group are asked to maintain their pre-study levels of physical activity and follow the recommendations provided by their physician. The study interventionist will contact control group participants each week to maintain ongoing communication about the study and inquire about any adverse events. After completing three-month measures, control group participants are provided with an in-home treadmill and individualized exercise program similar to that prescribed to the exercise group.

Month 3 Visit: The Month 3 Visit is a repeat of the Baseline Visit. At week 10 of the study, an accelerometer will be mailed to the participant with instructions for use. The participant will report to the inpatient unit after fasting for approximately 10 hours (minimum of 8 hours). The following will be completed:

- Weight and circumferences of the hip and waist
- Vital signs

- Concomitant medications
- Collection of accelerometer
- Females of child-bearing potential will complete a urine pregnancy test
- DXA*
- Oral glucose tolerance test (OGTT)**
- Submaximal fitness assessment
- Administer and review questionnaires

*After completing the DXA, the participant will be provided a snack prior to the fitness assessment.

**OGTT will take blood samples at 0, 60, and 120 minutes.

Upon completion of delivery and acceptance by the participant, the treadmill will be the participant's responsibility and will no longer be the responsibility of Pennington Biomedical Research Center or any of the researchers.

2. Procedure Descriptions

- Laboratory Collection. At baseline and three months, all participants will undergo a blood draw. Blood will be performed after fasting for approximately 10 hours (minimum of 8 hours), abstinence from alcohol consumption, and any structured exercise for 24 hours. 70 mL of blood will be collected, centrifuged, and aliquoted into 1.8 mL cryovials at 0.5 mL/vial. Whole blood, plasma, serum, and buffy coat will be collected. Blood samples will be stored at -80°C. Females of child-bearing potential will complete a urine pregnancy test.

Plasma Inflammatory Marker Concentrations.

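### With only two blood draws, the primary model uses baseline as both outcome and covariate: the adjustment drops out of the treatment estimate, and the 5% level depends on an unstated fitting choice

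*Combined protocol and SAP*

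**What the plan says.** The Laboratory Collection text under Procedure Descriptions gives two sampling times: "At baseline and three months, all participants will undergo a blood draw". Table 1 agrees.

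The Statistical Analysis section then sets out the model in three sentences:

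- "Changes in outcomes will be evaluated from baseline to follow-up in the two groups using a repeated-measures mixed-effects regression model"
- "The baseline value of the dependent variable and sex (randomization stratification factor) will be included as a covariate in the regression models"
- "Group-by-time interaction terms will be included as fixed effects in the regression model"

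It also says: "Plasma inflammatory concentrations will be log-transformed in the inferential analysis to improve normality". The two co-primary tests are "hierarchically ordered to test CRP and then IL-6 to maintain the overall experiment-wise error rate at 5" per cent, and the same techniques are reused for Aims 2 and 3. The section names no covariance structure, no degrees-of-freedom method, no baseline-by-time term and no explicit primary contrast.

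**The concern.** With a single post-baseline visit, a group-by-time term can be estimated only if the baseline value is one of the two outcome rows. The plan also puts that value on the right-hand side, and two things follow.

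First, the adjustment does not reach the treatment effect. The estimate reverts to a plain comparison of mean changes, without the precision and the correction for chance baseline imbalance that adjustment is meant to bring with 30 per arm.

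Second, the standard error depends on how the model is fitted. Because the covariance structure is left open, ordinary readings of the same text lead to an anticonservative test, a valid but less precise test, or a fit that breaks down. The closed testing procedure is meant to hold 5%, and CRP stands first in it, so under the global null the familywise error is whatever the CRP test delivers. The IL-6 rate matters only once CRP has been rejected.

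**Working it through.** **Inputs.** From the Power analysis section: CRP mean 1.87 mg/L, SD 1.32, "correlation of 0.8 between time points", reduction 0.71; IL-6 mean 1.7 pg/mL, SD 0.7, "a correlation of 0.58 between time points", reduction 0.57; 60 participants at 1:1, so 30 per arm. The 5% level is taken as two-sided, which the plan does not state.

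**The plan's own figures.** The SD of change is SD × √(2(1−r)): 1.32 × √0.40 = 0.835 mg/L for CRP and 0.7 × √0.84 = 0.642 pg/mL for IL-6.

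- CRP: 2 × (1.960 + 0.842)² × 0.835² / 0.71² = 21.7 per arm, or 44 in total. The noncentral t raises this to 46 (power 80.5%), the stated figure. The CRP sample size therefore already assumes a change-score analysis.
- IL-6: the stated 48 matches a follow-up-only normal formula that ignores r, 2 × 7.85 × 0.49 / 0.325 = 23.7 per arm. As a change score, 48 gives 85.4%.
- At 60 participants, change-score power is 90.0% (CRP) and 92.3% (IL-6).

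**Cancellation.** Let b be the common coefficient on baseline. It adds b × (difference in baseline means) to the group contrast at baseline and again at month 3. The group-by-time effect is the second contrast minus the first, so the term drops out whatever b is. Three simulated complete data sets gave interaction estimates of 0.0565, 0.1149 and −0.0287 with the covariate. These were identical to the raw differences in mean change. ANCOVA gave 0.0570, −0.0174 and −0.0720.

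**Precision lost.** In units of the outcome variance, change has variance 2(1−r) and ANCOVA has 1−r². The ratio is 2/(1+r): 1.11 at r = 0.8 and 1.27 at r = 0.58 in large samples. Simulation at 60 participants gives 1.09 and 1.24. Then 60/1.09 ≈ 55 and 60/1.24 ≈ 48 participants would give the same precision under ANCOVA.

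**Why the standard error can be too small.** Take unit variances. Pooled over both rows, the least-squares slope on baseline is b = (1+r)/2, the average of 1 (baseline row) and r (month-3 row).

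- The two residuals of one person then have covariance (1−b)(r−b) = −((1−r)/2)², which is negative. A random intercept whose variance cannot go below zero is pushed to zero.
- The mean residual variance is then (1−r)(3+r)/4. The model variance of the interaction is four times this over n per arm, (1−r)(3+r)/n. The true variance is 4(1−r)/n.
- The ratio is (3+r)/4: 0.95 (CRP) and 0.895 (IL-6). The large-sample type I error, 2 × [1 − Φ(1.96 × √ratio)], is 5.6% and 6.4%.

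**Simulation under the null** (60 participants, complete normal data, REML for two visits, at least 60,000 trials per correlation; ranges span separate runs):

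| | CRP, r = 0.8 | IL-6, r = 0.58 |
|---|---|---|
| Intercept variance at zero | 91% | 99.4% |
| Bounded random intercept, t with 58 df | 5.4–5.6% | 6.2–6.3% |
| Same, t with 114 df | 5.6–5.9% | 6.5–6.6% |
| Same, z | 6.1% | 6.7–6.8% |
| Change-score test, t with 58 df / z | 5.1% / 5.5% | 4.9% / 5.4% |
| ANCOVA, t with 56 df / z | 5.0% / 5.5% | 4.9% / 5.4% |

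With the reference distribution held fixed, double use of baseline adds about 0.6 points (CRP) and 1.2 points (IL-6). The rest of the z figures is z used in place of t.

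**Other fits.** Compound symmetry that allows negative covariance reproduces the change-score test and holds 5.0%. An unstructured fit has no maximum: as b approaches 1 every baseline residual goes to zero, and in one data set the log-likelihood climbed from 185 to 875.

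**Log scale.** The documents give no log-scale correlation. If values are lognormal with the stated means and SDs, it is ln(1 + r·CV²)/ln(1 + CV²), with CV = 1.32/1.87 and 0.7/1.7, giving about 0.83 and 0.60. The variance is then 7% and 23% larger than under ANCOVA, and the bounded fit has a type I error of 5.4–5.9% and 6.0–6.6%.

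**The case against.** The strongest reply is that the plan never says outright that baseline is an outcome row. The covariate sentence could mean ANCOVA on month 3, with the group-by-time wording left over from a template. On that reading precision is full and the error rate is 5%. But the repeated-measures and interaction sentences then cannot be carried out, so the text needs correcting on either reading.

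It is also fair to say that the inflation is small and conditional. It needs a random intercept bounded at zero and an analyst who accepts that fit. The problem would probably be seen: all 20 statsmodels fits to simulated data at r = 0.8 gave a boundary or singular-covariance warning, and the plan promises a check of model fit. It does not say what would be done next, so the remedy would be chosen after the data are in hand.

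Finally, no stated design target is missed. The change-score estimate is unbiased under randomisation, and the CRP sample size was built on it. That stands, but only for the raw-scale inputs; the documents give no log-scale SD or effect from which to check power on the analysis scale.

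**Conclusion.** The concern holds and should be fixed before analysis. As written, the model uses baseline twice. With complete data and no baseline-by-time term, the covariate has no effect on the group-by-time estimate, exactly and under any covariance structure. With missing month-3 values it has some influence; pilot dropout was 3%.

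Relative to ANCOVA, the cost in variance is 9% for CRP and 24% for IL-6 (7% and 23% at the assumed log-scale correlations). In power at 60 participants, this is 90% against 92–93% for CRP and 92% against 96–97% for IL-6, on raw-scale inputs.

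Whether 5% is held cannot be determined from the text. One common fit exceeds it mildly, by about 0.6 points for CRP, which governs the familywise rate under the global null, and by about 1.2 points for IL-6. The type I error figures assume normal, complete data.

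**What to change.** Use baseline once. Remove it as a covariate from the repeated-measures model, or drop the repeated-measures model. Name one of these:

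1. **Constrained longitudinal model.** Log baseline and log month-3 values are both outcomes, with a common baseline mean across arms, unstructured covariance, sex with its own effect at each visit, and group-by-month-3 as the treatment effect. State a small-sample degrees-of-freedom method.
2. **ANCOVA.** The log month-3 value is regressed on group, log baseline and sex, with a t reference on the residual degrees of freedom.

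Both are valid if month-3 values are missing at random given baseline, group and sex. With baseline complete they give the same treatment estimate: on 12 simulated data sets with 0% or about 10% of month-3 values missing, they agreed to six decimals.

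State the primary contrast explicitly, and carry the same wording to Aims 2 and 3. The cost is a change to the analysis text, with no new data or participants.
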